ADAS-Cog	Alzheimer's Disease Assessment Scale-Cognitive
ADCS-ADL MCI	Alzheimer's Disease Cooperative Study-Activities of Daily Living - MCI
AE	Adverse Event
AMCI	Amnesic Mild Cognitive Impairment
ANCOVA	Analysis of Covariance
APOE/APOE4	Apolipoprotein (APOE) Epsilon 4 (APOE4)
ATRI	Alzheimer's Therapeutic Research Institute
CDR-SB	Clinical Dementia Rating – Sum Of Boxes
CMRgl	Cerebral Metabolic Rate for glucose
CRF	Case Report Form
CSF	Cerebrospinal Fluid
DSMB	Data and Safety Monitoring Board
FDG	Fluoro Deoxy Glucose
FCSRT	Free And Cued Selective Reminding Test
mITT	modified Intention-To-Treat
MMSE	Mini- Mental State Examination
MRI	Magnetic Resonance Imaging
NPI	Neuropsychiatric Inventory
PBMC	Peripheral Blood Mononuclear Cell
PET	Positron-Emission Tomography
p-tau 181	phospho-tau 181
PK	Pharmacokinetic
SOP	Standard Operating Procedure
SAE	Serious Adverse Event
SAP	Statistical Analysis Plan
SPM	Statistical Parametric Mapping
sROI	statistical region of interest

3 Study Design/Summary

This section is from the Clinical Research Protocol, INI_Protocol_v5.0_20161205.pdf

3.1 Overview

The study will consist of a multisite, randomized, double-blind trial comparing the effects of INI (20 IU bid for total daily dose of 40 IU) and placebo for 12 months, followed by a 6-month open-label period in which all participants will receive INI. Participants with aMCI or probable mild AD (n=240-300) will be enrolled. The primary outcome measure will consist of the ADAS-Cog12. Secondary measures will include a memory composite, an executive function test, CDR Sum of Boxes (CDR-SB), and the ADCS-ADL MCI. The ADAS-Cog12 will be administered at 3 month intervals to optimize imputation of missing data. Other cognitive and functional measures will be administered at 6 month intervals. MRI measures of entorhinal cortex and hippocampal atrophy will be obtained at screening and 12 months. CSF and plasma biomarkers, as well as PBMcs and APOE- ϵ 4 allele carriage will also be assessed.

3.2 Study Aims

3.2.1 Primary Aim

To test the hypothesis that 12 months of treatment with INI (compared to placebo) in adults with aMCI and probable mild AD will improve performance on a global measure of cognition (ADAS- Cog12).

3.2.2 Secondary Aims

1. To test the hypothesis that 12 months of treatment with INI (compared to placebo) in adults with aMCI or probable mild AD will improve performance on a memory composite (Story Recall and FCSRT) and on daily function in adults with aMCI and probable mild AD.
2. To test the hypothesis that INI treatment reduces the rate of hippocampal and entorhinal atrophy as measured by MRI, and conduct exploratory analyses of other brain regions.
3. To test the hypothesis that INI will favorably alter CSF $A\beta$ and the CSF $A\beta$ /tau ratio, and will modulate inflammatory markers.
4. To examine whether baseline AD biomarker profile, APOE4 allele carriage and gender predict treatment response.
5. To determine whether further improvement occurs after 18 months of treatment.

3.3 Study Population

A total of 240-300 adults diagnosed with aMCI or probable mild AD will be enrolled in this trial. We expect to enroll no more than 50% of participants with probable mild AD and no more than 60% participants with aMCI diagnosis. To determine eligibility, all participants will undergo cognitive assessment, physical and neurological examination, ECG, clinical/safety laboratory assessment, and interviews of the participant and study partner.

3.5 Treatment Allocation

The two interventions are as follows:

- Group 1: active, 20 IU Humulin RU-100 bid for a total daily dose of 40 IU
- Group 2: placebo, matching placebo (sterile diluent)

Initially, eligible participants will be randomized on a 1:1 schedule to receive placebo or 20 IU bid of INI using the following randomization strategy:

- MMSE range (<=25 vs. >25)
- Site
- ApoE-e4 carrier status (yes or no)
- Gender (weight: 2)
- Age (<=70 vs. >70)

will be weighted in a covariate-adaptive randomization strategy to achieve optimal balance between treatment arms on important factors that may influence treatment outcome. After 12 months of double-blinded treatment with placebo or 20 IU bid of insulin, all participants will receive 20 IU INI bid in a 6-month, open-label extension.

4 Study Outcome Variables

4.1 Primary Outcome

Alzheimer's Disease Assessment Scale-Cognition 12 (ADAS-Cog12)

4.2 Secondary Outcomes

- CDR-SB
- memory composite (Immediate Paragraph Recall, Delayed Paragraph Recall and FCSRT)
- ADCS-ADL MCI

4.3 Safety Outcomes

- Adverse Events (AEs)
- Serious Adverse Events (SAE)
- Deaths
- Hospitalizations
- Vital Signs
- Standard Laboratory Tests

4.4 Biomarker and Imaging Outcomes

- MRI volumes (hippocampus, entorhinal cortex)
- $A\beta_{42}$, CSF total tau, p-tau 181, $A\beta_{42}/\text{tau}$, p-tau 181/ $A\beta_{42}$, $A\beta_{42}/A\beta_{40}$ ratio.

5 Sequence of Planned Analysis

5.1 Interim Analysis

AEs and SAEs are being monitored on a regular basis by a Data and Safety Monitoring Board (DSMB). There are no planned interim analysis being conducted for this study, but the DSMB may modify this during ongoing safety monitoring.

5.2 Final Analyses and Reporting

All final planned analyses identified in the research plan and in this SAP will be performed in two phases:

- blinded phase:
After the last participant has completed all assessments scheduled for blinded phase (12 months) of the study and the database for this phase has been cleaned and locked. This analysis will only include visits up to and including 12 months.
- follow-up phase:
After the last participant has completed assessments scheduled for the study (18 months) and the complete database has been cleaned and locked. This analysis will only include visits up to and including 18 months.

Any post-hoc exploratory analyses performed to provide support for planned analyses but not identified in this SAP will be documented and clearly identified as unplanned analysis in the manuscript.

6 Statistical Methods

6.1 Analysis Populations

- Intent-to-treat (ITT) population: All eligible individuals who are randomized.
- Modified ITT (mITT) population: Subjects who are randomized and have at least one post-baseline assessment.
- Compliance population: Subjects complete the study on treatment with $\geq 80\%$ treatment compliance based on study diary.

6.2 Multiple-testing Strategy

We propose a multiple-testing strategy using a basic serial gatekeeping procedure to maintain over-all experiment-wise Type I error at $\alpha = 0.05$ (two-sided). The four hypotheses regarding (i) ADAS-Cog12, (ii) CDR-SB, (iii) memory composite (Immediate Paragraph Recall, Delayed Paragraph Recall and FCSRT), (iv) ADCS-ADL MCI will be tested in order using a basic serial testing strategy. If, for example, $p_{ADAS} \geq 0.05$, no subsequent hypotheses will be declared statistically significant. Otherwise if $p_{ADAS} < 0.05$, the CDR-SB hypothesis is tested by comparing p_{CDR} to 0.05. This strategy continues until a p -value is ≥ 0.05 , or the ADCS-ADL MCI hypothesis is declared statistically significant with $p_{ADL} < 0.05$.

Regardless of the outcome of the multiple testing strategy, p -values and 95% confidence intervals will be reported for all planned analyses.

6.3 Incomplete Follow-up/ Missing Data

- If any of the individual items for the clinical outcomes are missing, every effort will be made to obtain the score for the missing item or items.
- ADAS-Cog12 and CDRSB Scoring: Total scores for assessments with missing item scores will be imputed using a proration strategy. If the maximum score with the non-missing items represents $\geq 70\%$ of maximum possible total score, the total score will be imputed. The score observed with the non-missing items will be prorated to the score with all items, as follows:

$$\text{Imputed score} = \text{Maximum score with all items} \times \frac{\text{Score observed with non-missing items}}{\text{Maximum score with non-missing items}}$$

The imputed score will be rounded to the nearest integer. If the maximum score with the non-missing items represents $< 70\%$ of the maximum score with all items, the total score for the assessment at that visit will not be imputed and will be considered missing.

- ADCS-ADL MCI Scoring: The response of "Don't Know" for any individual question will be scored as 0 (the same score as response of "no").
- FCSRT scoring: Sum of total free and total cued recall score. The score is missing if cued recall is missing.
- Memory Composite (Immediate Paragraph Recall, Delayed Paragraph Recall and FCSRT): Each of the three component scores is divided by the baseline sample standard deviation of that component to form standardized Z scores. Three Z scores are summed to form the memory composite. If any of Immediate Paragraph Recall, Delayed Paragraph Recall and FCSRT is missing, the memory composite is missing.

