### 3.5 Results: Cognitive and Functional Outcome Measures

The three groups did not differ at baseline on any outcome measure; change from baseline is represented in figures for ease of interpretation. A significant overall treatment group by time interaction was observed for primary outcome delayed story recall ( $p=0.005$ ). Compared to placebo, the low dose group had improved delayed recall (Fig. 2A; treatment by time  $p=0.02$ , Cohen's  $f^2=0.36$ ), whereas no effect was observed for the high dose group. Exploratory post-hoc analyses were then conducted to more closely examine the relationship of insulin dose to story recall, as this was a primary goal of this pilot clinical trial. Given findings that delayed recall may not be a sensitive measure for AD subjects due to increased variability and floor effects (Sano, Raman et al. 2011) we constructed a total story recall score (immediate and delayed), which showed improvement for the high-dose group (time by treatment interaction  $p<0.05$ , mean log total story recall change score with SEM =  $-.15(.1)$  for placebo vs.  $.12 (.09)$  for the high dose group). A significant overall treatment by time interaction was observed for the other primary outcome measure, the DSRS ( $p=0.008$ ). Compared with placebo, DSRS scores were preserved for both low and high dose groups (Fig. 2B; treatment by time  $ps=0.01$  and  $0.01$ , Cohen's  $f^2=0.38$  and  $0.41$ ). For secondary measures, significant effects were observed for the ADAS-Cog (overall treatment by time interaction  $p=0.004$ ). Both low and high insulin groups had less decline in cognition compared with placebo (Fig. 2C; treatment by time  $ps=0.04$  and  $p=0.002$ , Cohen's  $f^2=0.27$  and  $.40$ ). Treatment effects on the ADAS-Cog interacted with age; for the high dose insulin group, greater improvement (lowered score) tended to be associated with younger age ( $r=.31$ ,  $p=0.06$ ). For the ADCS-ADL, no overall effects of treatment on daily function were observed. However, a significant interaction with diagnosis was observed for this measure (overall treatment by time by diagnosis interaction  $p=0.02$ ). Participants with AD receiving either dose of insulin had preserved function compared with placebo-assigned participants with AD who showed slight decline, whereas participants with aMCI showed no change regardless of treatment assignment (interactions for the participants with AD in low and high dose groups compared with placebo,  $ps=0.01$  and  $0.02$ , Cohen's  $f=0.45$  and  $0.43$ ; Fig. 2D). Adjustment for APOE- $\epsilon 4$  status, baseline MMSE score, cholinesterase inhibitor treatment, gender, and education did not affect the pattern of any result.

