## 9.0 STUDY-SPECIFIC PROCEDURES

### 9.1 Cognitive Evaluations

#### 9.1.1 Alzheimer's Disease Assessment Scale-Cognitive (ADAS-Cog12)

The ADAS-Cog (Rosen, Mohs et al. 1984) is a psychometric instrument that evaluates memory, attention, reasoning, language, orientation, and praxis. A higher score indicates more impairment. Scores from the original portion of the test range from 0 (best) to 70 (worse) and then number of items not recalled ranging from 0-10 is added for a maximum score of 80. A positive change indicates cognitive worsening. An ADAS-Cog12 version will be used in the current study which includes Delayed Word Recall - a measure of episodic memory (Mohs, Knopman et al. 1997). The ADAS-Cog has been the primary cognitive instrument in previous and ongoing Alzheimer's Disease therapeutic trials. Neuropsychometrists at each site are required to complete an ADAScog training and certification process. The person administering this test should not also administer the CDR.

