### **9.2 Clinical and Functional Evaluations**

#### **9.2.1 Clinical Dementia Rating Scale – Sum of Boxes (CDR-SB)**

The CDR (Hughes, Berg et al. 1982; Morris 1993) is a clinical scale that rates the severity of dementia as absent, questionable, mild, moderate, or severe (CDR score of 0, 0.5, 1, 2, or 3, respectively). The score is based on interviews with the participant and study partner, using a structured interview that assesses six domains: memory, orientation, judgment and problem solving, community affairs, home and hobbies, and personal care.

At Screening the CDR global score will be used for eligibility purposes. For all other administrations, the 6 domain scores will be summed to get the Sum of Boxes (SB) score. Training on the use of the CDR will be conducted to standardize its administration across sites. The CDR online training tool resides on the Washington University, St. Louis website, with oversight provided by [name] (Morris, Ernesto et al. 1997). The person administering the CDR should not also administer the ADAS-Cog12.

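### Prorated CDR-SB totals are rounded to whole points although the scale moves in half points: a small, avoidable scoring error in SAP 6.3

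*SAP*

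**What the plan says.** SAP 6.3 has one bullet for ADAS-Cog12 and CDR-SB together: "Total scores for assessments with missing item scores will be imputed using a proration strategy". The observed score is multiplied by the full maximum over the maximum of the items present, provided those items carry at least 70% of the full maximum. Below that share, the total for the visit is missing. The bullet then adds "The imputed score will be rounded to the nearest integer", with no exception for either scale. Before any of this, the section asks sites to try to obtain the missing item.

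Protocol 9.2.1 gives the rating levels as "CDR score of 0, 0.5, 1, 2, or 3, respectively" and says that, after screening, "the 6 domain scores will be summed to get the Sum of Boxes (SB) score". SAP 6.2 tests CDR-SB second, directly after ADAS-Cog12. SAP 7.5 analyses it with an MMRM like the primary one, which models change from baseline.

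**The concern.** A scale built from six ratings that include 0.5 takes half-point values. Rounding a prorated total to a whole number discards resolution that every complete record keeps. In a change-score analysis, a participant can have one visit scored on the half-point grid and another on the whole-point grid. A rounding error in the baseline record also passes into each later change for that participant.

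The setting is what makes this worth correcting. CDR-SB is the first gated secondary, so if it fails, the memory composite and ADCS-ADL MCI cannot be declared significant. The documents give no reason for the coarser grid.

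**Working it through.** **Inputs**
- CDR levels 0, 0.5, 1, 2, 3 (Protocol 9.2.1). The protocol gives them for the CDR score. That each box uses the same levels is an inference.
- Six boxes summed (Protocol 9.2.1). The maximum is therefore 6 × 3 = 18, which is derived and not stated.
- Proration formula, 70% limit and integer rounding (SAP 6.3).

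**Check of a stated maximum.** Protocol 9.1.1 gives an ADAS-Cog12 maximum of 80, and 70 + 10 = 80. No maximum is stated for CDR-SB.

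**When the rule acts on CDR-SB**
- One box missing: 15/18 = 83.3%, so the total is prorated.
- Two boxes missing: 12/18 = 66.7%, so the total is missing.

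Only records with exactly one missing box are affected.

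**What rounding does.** With an observed five-box sum s, the prorated score is 18/15 × s = 1.2 s.

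| s | 1.2 s | stored under SAP 6.3 | error | nearest 0.5 | error |
|---|---|---|---|---|---|
| 0.5 | 0.6 | 1 | +0.4 | 0.5 | −0.1 |
| 1.0 | 1.2 | 1 | −0.2 | 1.0 | −0.2 |
| 1.5 | 1.8 | 2 | +0.2 | 2.0 | +0.2 |
| 2.0 | 2.4 | 2 | −0.4 | 2.5 | +0.1 |
| 2.5 | 3.0 | 3 | 0 | 3.0 | 0 |
| 3.0 | 3.6 | 4 | +0.4 | 3.5 | −0.1 |
| 3.5 | 4.2 | 4 | −0.2 | 4.0 | −0.2 |
| 4.0 | 4.8 | 5 | +0.2 | 5.0 | +0.2 |
| 4.5 | 5.4 | 5 | −0.4 | 5.5 | +0.1 |
| 5.0 | 6.0 | 6 | 0 | 6.0 | 0 |
| 5.5 | 6.6 | 7 | +0.4 | 6.5 | −0.1 |
| 6.0 | 7.2 | 7 | −0.2 | 7.0 | −0.2 |

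Errors are measured against the prorated value 1.2 s.
- The two rules differ, by 0.5, in 5 of 12 rows (s = 0.5, 2.0, 3.0, 4.5, 5.5): three upward and two downward.
- Mean absolute error is (5 × 0.4 + 5 × 0.2)/12 = 0.25 with integers and (5 × 0.1 + 5 × 0.2)/12 = 0.125 with half points.
- The largest error is 0.4 against 0.2. These maxima hold over all 29 attainable five-box sums, of which 11 differ between the rules.
- The integer errors repeat every five rows (+0.4, −0.2, +0.2, −0.4, 0) and sum to zero over a cycle.

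**Scale at arm level.** If a share f of one arm's records at a visit is prorated, rounding can move that arm's raw mean by at most 0.4 f, and only if every error has the same sign. For assumed f of 2% and 5%, the bound is 0.4 × 0.02 = 0.008 and 0.4 × 0.05 = 0.02 point. The documents give no value of f.

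**The case against.** The strongest reply is that this hardly matters. Complete assessments are untouched, sites must first try to recover the item, and two missing boxes already make the total missing. The missing box could lie anywhere from 0 to 3, which is a larger uncertainty than 0.4. The half-point value is not a known true score either. The stored integers can also be legitimate totals: 2.0 stored as 2 implies a missing box of 0, and 3.0 stored as 4 implies a box of 1. The errors go both ways.

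All of this stands, and it limits the size of the point. It does not justify the rule: the rounding adds error on top of the proration, and nothing is gained from it.

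A reader might also infer that the same bullet biases the primary endpoint. Without Delayed Word Recall, 70/80 = 87.5% of the ADAS-Cog12 maximum remains (the item "number of items not recalled ranging from 0-10 is added for a maximum score of 80"), so the total is prorated. With S observed on the other items, the missing item is filled with 80S/70 − S = S/7. At S = 20 that is 2.9, and the total is stored as 23. If the true item score were 6, 8 or 10 (assumed), the total would be 3, 5 or 7 points too low. The error vanishes when the true item is near S/7 and reverses below it: at S = 35 the fill is 5, and a true item of 4 makes the total 1 point too high.

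The documents do not settle which case applies, since they give no item-level scores. The remark in Protocol 3.5 that "delayed recall may not be a sensitive measure for AD subjects due to increased variability and floor effects" explains why the pilot combined immediate and delayed story recall. It is limited to AD subjects, whereas up to 60% of this sample may have aMCI (Protocol 5.1). Nor should such single-record errors be read against the 1.6 to 2.6 point between-arm differences in Protocol 12.1: a bias between arms would need prorated records to differ between arms, and the documents do not suggest that they do. Setting the total to missing would discard 70 of 80 possible points and rely on the MMRM's missing-data assumption instead, a trade-off on which statisticians can differ.

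**Conclusion.** The integer-rounding sentence does not fit CDR-SB and should be changed. It adds up to 0.4 point, in either direction, to records with exactly one unrecovered missing box, and it scores those records on a different grid from complete ones. This rests on two inferences from Protocol 9.2.1: that the boxes use the listed CDR levels, and that the maximum is 18.

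It would be too strong to say that the rule gives wrong scores on the gated endpoints generally, or that it threatens the CDR-SB test. Only prorated records are affected, no directional shift is shown, and without an item-missing rate the effect on the test cannot be estimated. It is probably small. The ADAS-Cog12 observation is conditional on the unknown item score and does not support a required change.

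**What to change.** In SAP 6.3, either delete the rounding sentence or replace it with a rule that prorated CDR-SB totals are rounded to the nearest 0.5. Deletion removes the rounding error altogether and leaves some values between grid points, such as 2.4, which the MMRM can take as they are. Half-point rounding keeps prorated and complete records on one grid, with an error of at most 0.2. Either choice is acceptable.

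The cost is one sentence in the SAP. Data collection, sample size and the testing order do not change. If the sentence is deleted outright, prorated ADAS-Cog12 totals also become unrounded, and the team should confirm that this is intended. No change to how ADAS-Cog12 handles a missing Delayed Word Recall is asked for.

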6.4 Covariates

Covariates to be included are specified for each analysis, when applicable.

6.5 Data Management and Analysis Software

Most data manipulation, tables, figures, listings and analyses will be created using R programs and performed using R statistical software (<http://www.r-project.org>). R version used will be specified in the analysis reports.

7 Statistical Analysis

7.1 Study Flow

A CONSORT style flow diagram will illustrate patient progression through the trial from initial screening for eligibility to completion of the final primary outcome assessment. Number (percentage) will be included for subjects screened, screen failed (with reasons), randomized, study discontinued (with reasons), treatment discontinued (with reasons), analyzed, excluded from analysis (with reasons). The diagram will be separated by treatment groups starting from randomization.

7.2 Visit Windows

As subjects do not always adhere to the protocol visit schedule, the following rules are applied to assign actual visits to analysis visits. Listed below are the visit windows and the target days for each visit. The reference day is Study Day 1. If a subject has 2 or more actual visits in one visit window, the visit closest to the target day will be used as the protocol visit for that visit window. Listed below (Table 2) are the visit windows and the target days for each visit defined in the protocol.

Table 2: Visit Windows for Analysis

Visit Code	Time Interval (days)	Target (days)
bl	(-30, 1)	1
m03	(2, 136)	91
m06	(137, 225)	181
m09	(226, 315)	271
m12	(316, 379)	366
m15	(380, 502)	458
m18	(503, 554)	541

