#### 4.4 Rationale for Length and Design of Trial

In the pilot study (Craft, Baker et al. 2012), beneficial effects of insulin on cognition, function and cerebral glucose metabolism were detected in a 4-month period. The current study design will extend the treatment period to a year for primary analyses, which should be sufficient to detect clear changes in memory and imaging endpoints for both aMCI and AD groups. The additional 6-month, open-label extension used in this semi-crossover design may incentivize participants to enroll and remain in the trial, and also provide added power for safety analyses (Jarjoura 2003). Exploratory efficacy analyses may also provide useful information, although these results will need to be interpreted with caution in light of their unblinded status.

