### **7.8 Month 15 (Visit 7, Open Label)**

The Month 15 visit is scheduled 15 months (+/- 2 weeks) from day one of the Baseline visit. At the Month 15 visit, the ADAS-Cog12 will be administered. In addition, vital signs and weight will be obtained, a nasal examination will be conducted, adverse events and concurrent medications will be recorded. Participants will bring their device, study diary and any used and unused study drug vials to the site. Study drug compliance will be assessed. POD components (actuators, vial adapters, canisters and POD tips) will be dispensed.

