## 7.9 Month 18 (Visit 8, Open Label)

The Month 18 visit is scheduled 18 months (+/- 2 weeks) from day one of the Baseline visit. At the final Month 18 visit, plasma insulin, glucose, A $\beta$ 40 and A $\beta$ 42 should be measured in the morning after an overnight fast, if possible. Additional plasma, along with serum and peripheral blood mononuclear cells (PBMCs) will be collected and banked. Clinical laboratory evaluations will be conducted to monitor safety and tolerability.

Cognitive and behavioral assessments will be performed (during a non- fasting session). The study procedures will be standardized such that the ADAS-Cog12 will be the first cognitive test administered. Additional assessments include the MMSE, memory composite (Story Recall and FCSRT), Trail-making Test part A and B, CDR-SB, the ADCS-ADL-MCI and NPI. The Research Satisfaction Survey will also be administered.

In addition, vital signs and weight will be obtained, physical, neurological and nasal examinations will be conducted, adverse events and concurrent medications will be recorded and study drug compliance will be assessed. Participants will return their study diary, their Impel POD device components, and any used and unused study drug vials to the clinic. Study drug compliance will be assessed during this final visit.

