7.4 Analysis of Primary outcome

Individuals in the active arm with Impel device will demonstrate slower rate of decline on ADAS-Cog12 in comparison to the placebo arm. Mixed Model repeated measures analysis of variance (MMRM) will be used to assess the difference between treatment groups in change from baseline for performance on the ADAS-Cog12. Participants will be included in the model if they have both a baseline and at least one post-baseline ADAS-Cog12. Change from baseline at each post-baseline visit for the ADAS-Cog12 will be the dependent variable. We will use a heterogeneous autoregressive AR(1) covariance structure. If the heterogeneous AR(1) covariance structure results in a lack of convergence, the following covariance structures will be used in sequence: heterogeneous compound symmetry covariance, homogeneous autoregressive AR(1) covariance, homogeneous compound symmetry covariance. Fixed effects in the model will include the following terms: (i) baseline ADAS-Cog12 score, (ii) treatment, (iii) visit, (iv) treatment-by-visit interaction, and (v) APOE- ϵ 4 genotype (Y/N) (vi) gender (vii) baseline MMSE score (viii) baseline age. Visits (baseline, month 3, month 6, month 9 and month 12) will be treated as a categorical variable. The null hypothesis is that the treatment difference between active and placebo with Impel device for the ADAS-Cog12 at month 12 is equal to zero.

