7.5 Analysis of Secondary Outcomes

Secondary Aims I

Individuals in the active arm with Impel device will demonstrate slower rate of decline on secondary outcomes including CDR-SB, memory composite (Story Recall and FCSRT), and ADCS-ADL MCI in comparison to the placebo arm. Mixed Model repeated measures (MMRM) models similar to the primary analysis will be used.

Secondary Aims V

To determine whether further improvement occurs after 18 months of treatment.

- The analysis will be the same as the primary analysis with data up to the month 18. The null hypothesis is that the treatment difference between active and placebo with Impel device for the ADAS-Cog12 at month 18 is equal to zero.
- Delayed-start analysis is to compare Δ_2 , the treatment differences between active and placebo at the month 18 (delayed-start period) with Δ_1 that at the end of the placebo-controlled period with noninferiority margin as 50% of Δ_1 [1, 2].

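### The SAP's last analysis window, m18, closes at Day 554, before the protocol's Month 18 visit allowance ends, so some compliant Month 18 scores have no analysis visit

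*SAP*

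**What the plan says.** SAP 7.2 assigns actual visits to analysis visits by study day. It states that "The reference day is Study Day 1" but does not tie that day to an event. It then says: "Listed below (Table 2) are the visit windows and the target days for each visit defined in the protocol". The rows that matter here are:

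| Row | Window (days) | Target |
|---|---|---|
| bl | -30 to 1 | 1 |
| m03 | 2 to 136 | 91 |
| m12 | 316 to 379 | 366 |
| m15 | 380 to 502 | 458 |
| m18 | 503 to 554 | 541 |

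If two visits share a window, the one nearer the target is used. There is no rule for a visit that falls in no window.

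The protocol schedules visits by elapsed months. For Month 18, section 7.9 says: "The Month 18 visit is scheduled 18 months (+/- 2 weeks) from day one of the Baseline visit". Section 7.8 uses the same form for Month 15: "The Month 15 visit is scheduled 15 months (+/- 2 weeks) from day one of the Baseline visit". Section 7.7 does so for Month 12.

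The primary model in SAP 7.4 is by visit: "Visits (baseline, month 3, month 6, month 9 and month 12) will be treated as a categorical variable". For Secondary Aim 5, SAP 7.5 extends it: "The analysis will be the same as the primary analysis with data up to the month 18". It adds a delayed-start comparison that also uses the Month 18 treatment difference.

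**The concern.** An analysis window should be at least as wide as the visit allowance it serves. The m18 window is narrower at its late end. It is also the last row, so a late Month 18 visit has no neighbouring window to fall into.

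Because visit is categorical, a score without an analysis visit has no place in the model. A Month 18 assessment made on time under the protocol could then be missing from both planned analyses of Secondary Aim 5. Otherwise the analysts would have to invent a rule after the data are in. A smaller version of the same mismatch affects Month 12, which carries the primary contrast.

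**Working it through.** **1. The SAP's own figures.** The m18 target is 18 x 30 + 1 = 541, and its upper limit is 540 + 14 = 554. The m12 limit has the same form: 365 + 14 = 379. Targets m03, m06 and m09 (91, 181, 271) are also 30-day months plus 1. Targets m12 (366) and m15 (458) fit calendar months instead. Adjacent rows end at 502 and start at 503, so the limits are inclusive.

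**2. The protocol's Month 18 allowance, with Study Day 1 as day one of Baseline.** Every start date from 2012 to 2019 was enumerated.

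- 18 calendar months = 546-550 elapsed days, which is Day 547-551.
- Permitted days: 14 + 1 + 14 = 29.
- Last permitted day: 547 + 14 = 561 to 551 + 14 = 565.
- Days after the window closes: 561 - 554 = 7 to 565 - 554 = 11. The value 11 needs a leap day in the span.
- First permitted day: 547 - 14 = 533 or later, well after Day 503. Nothing is lost at the early end.

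Protocol 12.0 converts at 30.5 days per month: 18 x 30.5 = 549 days, which is Day 550. The allowance then ends on Day 564, leaving 10 days out.

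**3. Sensitivity to the anchor.** Protocol 7.3 lets Baseline take up to seven days and places it before any study drug, so Study Day 1 could fall after day one of Baseline. Each day of shift removes one day from the gap.

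| Study Day 1 after day one of Baseline | Days outside, calendar months | 30.5-day months | 540 days |
|---|---|---|---|
| 0 days | 7-11 | 10 | 1 |
| 1 day | 6-10 | 9 | 0 |
| 3 days | 4-8 | 7 | 0 |
| 6 days | 1-5 | 4 | 0 |
| 7 days | 0-4 | 3 | 0 |

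Over shifts of 1-6 days the calendar range is 1-10.

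**4. Other windows, no shift.** Twelve months is Day 366-367, so the allowance ends on Day 380-381, and 380 - 379 = 1 to 381 - 379 = 2 days are labelled m15. With a one-day shift this is 0-1 day, and with a larger shift none. The m03, m06, m09 and m15 windows all extend at least 24 days beyond the end of the allowance.

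**5. From days to participants.** The documents give no visit timing, so any share is an assumption. The shares below take on-schedule visits centred on the 18-month date and truncated at 14 days either side.

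| Assumed timing | Share after Day 554, no shift | Share, six-day shift |
|---|---|---|
| Uniform | 30% | 10% |
| Normal, SD 7 days | 20% | 3% |
| Normal, SD 5 days | 13% | 1% |
| Normal, SD 3 days | 4% | under 0.1% |

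**6. A check on the remedy.** If Study Day 1 is day one of Baseline and bl stays at -30 to 1, an ADAS-Cog12 done on Days 2-7 of a permitted seven-day Baseline visit is labelled m03. SAP 7.4 requires a baseline score for entry to the primary model. Fixing the anchor without changing the bl and m03 rows would therefore put primary data at risk.

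**The case against.** The strongest objection concerns size. The 7-11 figure depends on an anchor that the SAP does not state. The bl row fits day one of Baseline poorly when Baseline takes several days, and a later anchor narrows the gap. This stands, and it is why the result is given as a range. On calendar months, though, the gap stays open for every shift of 1-6 days.

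The m18 target may also follow a deliberate 30-day rule, as m03, m06 and m09 do. That is fair: m18 is not the only row built this way. It is also fair that target + 14 = Day 555 misses the window by only a one-day counting convention, which is not separate evidence of a fault. But the early rows have wide late margins that absorb the difference, and m18 does not. The protocol's own 30.5-day month gives a gap of 10 days with no shift.

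Exclusion is inferred, since the SAP is silent on visits outside every window. That is correct. The silence is part of the defect, because a categorical model needs a label.

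SAP 5.2 might be read as intending a cut-off: "This analysis will only include visits up to and including 18 months". With no shift, however, the m18 window itself runs 3-7 days past the 18-month date (554 - 551 to 554 - 547). The sentence is better read as naming the last scheduled visit.

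Finally, the consequence is modest. Aim 5 is outside the sequence in SAP 6.2, and protocol 4.4 says of open-label efficacy that "these results will need to be interpreted with caution in light of their unblinded status". That stands.

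**Conclusion.** The mismatch is real. With calendar months and Study Day 1 as day one of Baseline, 7-11 of 29 permitted Month 18 days have no analysis visit. The gap is 1-10 days if Study Day 1 is 1-6 days later, 0-4 at seven days, and at most 1 day if 18 months means 540 days.

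Three stronger readings are tempting, and the documents do not support them.

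- A reader might infer that the Month 18 comparison is biased. The windows are the same in both arms, and the model keeps each participant's earlier visits. Nothing shows that late attendance differs by arm.
- A reader might infer that a known share of participants is lost. The counts are days, and the shares rest wholly on assumed timing.
- A reader might infer that the primary analysis is compromised. The Month 12 overlap is 1-2 days with no shift, 0-1 with a one-day shift, and none beyond that.

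What remains is an avoidable loss of usable Month 18 data, of unknown size, in Secondary Aim 5. It should be corrected because the correction is cheap.

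**What to change.** Revise SAP Table 2 and its introduction together, before database lock:

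- Define Study Day 1 by a named event.
- Extend the m18 upper limit to at least Day 565. This covers the protocol allowance whether Study Day 1 is day one of Baseline or later. Align the m18 target with 18 months, which is about Day 549 if Study Day 1 is day one of Baseline.
- Extend m12 to at least Day 381 and start m15 on the following day. Keep in m12 only assessments made before the first open-label dose.
- In the same revision, change bl and m03 so that any assessment made before the first dose within the seven-day Baseline visit is assigned to bl.
- State how a visit outside every window is handled.

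The cost is five table rows and a few sentences, with no new data and no change to any visit. The downside is that a few slightly later scores enter m12 and m18.
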